## PROCESS EVALUATION OF IMPLEMENTATION

We will track participation and completion rates for purposes of evaluating implementation. These rates will be utilized to establish overall CPOP implementation fidelity and overall rate of assessment procedure completion. (See Section 11

### Statistical Considerations)

Components of implementation	Definition of components  (Based on Linnan and Steckler, 2002)
Reach (Recruitment/Participation rate)	The proportion of women who are recruited, enrolled, and participate out of all invited women
Dose delivered (Delivery rate)	CPOP modules - proportion of planned sessions that were conducted
Dose received (Attendance rate)	Proportion of the CPOP modules that participants received
Fidelity (Estimated fidelity rate)	Proportion of the learning objectives addressed in the CPOP modules

## **8.2      Laboratory Procedures/Evaluations**

### ***8.2.1    Clinical Laboratory Evaluations***

None

### ***8.2.2    Special Assays or Procedures - Salivary bacterial analysis***

Microbiological assays: Salivary assays will be performed under the guidance of [name] in her laboratory at UCSF. Maternal and infant saliva will be assayed for *Mutans Streptococci* (MS), *Lactobacillus* (LB), and Total Viable Count (TVC).

### ***8.2.3    Specimen Preparation, Handling, and Storage***

Saliva specimen storage, handling and banking for future studies: Each saliva sample will be labeled with study ID and collection date. Once transported to the microbiology lab, the samples will be plated immediately or stored in a 4° refrigerator for plating within 24 hours, all under the care and supervision of [name]. The saliva samples will be destroyed according to biological hazardous waste guidelines immediately following the microbiological assays. The access to the samples will be logged in a laboratory log sheet. No saliva will be banked for future studies.

### ***8.2.4    Specimen Shipment***

Specimens will not be shipped

## **9. ASSESSMENT OF SAFETY**

### **9.1      Specification of Safety Parameters**

Because participants represent vulnerable populations, special attention will be given to any adverse events that occur during the study. The CPOP takes place in the health care setting in which participants receive their prenatal care. The CP facilitator who conducts the CPOP intervention in each CP group (participant's prenatal care provider) will be present and aware of each woman's physical condition during the CPOP study. Safety reporting for the study will focus on serious adverse events (SAEs) or unanticipated problems related to study interventions that occur during the course of the study.

#### ***9.1.1    Unanticipated Problems (UP)***

The Office for Human Research Protections (OHRP) considers unanticipated problems (UPs) involving risks to subjects or others to include, in general, any incident, experience, or outcome that meets **all** of the following criteria:

- unexpected in terms of nature, severity, or frequency given (a) the research procedures that are described in the protocol-related documents, such as the IRB-approved research protocol and informed consent document; and (b) the characteristics of the subject population being studied;
- related or possibly related to participation in the research (“possibly related” means there is a reasonable possibility that the incident, experience, or outcome may have been caused by the procedures involved in the research); and
- suggests that the research places subjects or others at a greater risk of harm (including physical, psychological, economic, or social harm) than was previously known or recognized.

### **9.1.2 Adverse Events**

An AE is any untoward or unfavorable medical occurrence in a human subject, including any abnormal sign (for example, abnormal physical exam or laboratory finding), symptom, or disease, temporally associated with the subject’s participation in the research, whether or not considered related to the subject’s participation in the research.

AEs will be recorded and monitored to ascertain their frequency, severity, and nature, to determine whether they are related to study activities, and thus would reflect an Unanticipated Problem, which would be reported.

### **9.1.3 Serious Adverse Events**

A serious adverse event (SAE) is one that meets one or more of the following criteria:

- Results in death
- Is life-threatening (places the subject at immediate risk of death from the event as it occurred)
- Results in inpatient hospitalization or prolongation of existing hospitalization
- Results in a persistent or significant disability or incapacity
- Results in a congenital anomaly or birth defect
- An important medical or dental event that may not result in death, be life threatening, or require hospitalization may be considered an SAE when, based upon appropriate medical judgment, the event may jeopardize the subject and may require medical or surgical intervention to prevent one of the outcomes listed in this definition.

## **9.2 Time Period and Frequency for Event Assessment and Follow-Up**

UPs will be recorded in the data collection system throughout the study.

The PI will record all events with start dates occurring any time after informed consent is obtained until 7 (for non-serious AEs) or 30 days (for SAEs) after the last day of study participation. At each study visit, the investigator will inquire about the occurrence of AE/SAEs since the last visit. Events will be followed for outcome information until resolution or stabilization.

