When an infant is approximately 10 months of age, study staff will contact families to remind them of the final assessment to take place at infant age 12 months. We will assess eligibility of the infant to participate in the follow-up and confirm mother's intention to complete the final assessment. If the infant is ineligible to participate, the mother will still be eligible to complete the final assessment. The 12-month visit time will be scheduled.

The 12-month visit will occur at the participant's home or another location that is convenient for the mother and baby. Women will complete questionnaires and saliva collection procedures for assessment of salivary bacteria. The infants will complete a saliva collection procedure. Women receive their incentives within a week following completion of the assessments.

CP Facilitator participants: The CP facilitators will complete assessments of acceptability and feasibility of the CPOP Intervention at the time that study activities have come to a close in their clinics. This will include evaluation of their: satisfaction with the training and the amount of time taken to prepare for and implement the CPOP modules in their

groups; perceived value of CPOP to CP moms; perceived scalability of the interventions into the broader standard CP curriculum; and overall perceptions of the benefits versus burdens associated with the changes needed to accommodate CPOP modules in CP sessions. These data will help inform future implementation when CPOP is scaled up and disseminated broadly. These will be done online through REDCap.

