## **5. STUDY ENROLLMENT AND WITHDRAWAL**

### **5.1 Subject Inclusion Criteria**

CP Facilitators:

- CP facilitators who conduct CP groups within the 5 designated study sites;
- ages 18 and older speak, read, and write in English;
- provide informed consent

CP Women:

- speak, read, or write in English or Spanish
- enrolled in CP prenatal group care identified as study groups
- free of any condition that requires them to take antibiotic or antibacterial medication prior to dental procedures
- provide informed consent

CP Babies:

- healthy with no acute or chronic medical conditions, especially those conditions that may have resulted in hospitalizations and subsequent exposure to pathologic microorganisms
- mothers provide informed consent for their children at baseline

Dental Exam Calibration Participants:

- ages 18 and older
- free of any condition that requires them to take antibiotic or antibacterial medication prior to dental procedures
- provide informed consent

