### 7.3 Intermediate Visits

#### 7.3.1 Visit 2 (Day 14 ± 14) Maternal Intervention Administration

The range of +/- days is broad because the baseline data could be collected in a range of approximately 28 days between CP sessions 2 and 3, but prior to the administration of the CPOP Maternal Module in CP Session 3.

- Takes place among participants in the Intervention arm only

- Administer the maternal OH module in Intervention Arm
- Record participation and attendance at the intervention

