#### **7.3.3 Visit 4 (Day 90 +/- 21) Administer Infant Module in Intervention Arms**

- Administer Infant Intervention
- Record attendance

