### **7.5 Withdrawal Visit**

Women who withdraw from the study will be queried to determine their reasons for withdrawal.

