## 12.2 Sample Size Considerations

**Sample size estimate and power analyses.** We assume 80% power; two-tailed  $\alpha=0.05$ ; 75% retention at 12 months; binary outcomes describing maternal gingival 1) pocket depth  $\geq 4$ mm (PD4) and 2) bleeding on probing (BOP) at each probed site (max=168; in pilot data  $\bar{x}=159$  sites per participant); 3) a continuously coded maternal plaque index score (PI: range 0-4); and 4) a child-level binary MS colonization indicator. The PD4 and BOP data for mothers will have a 5-level nested structure with a) 5 CP sites, b) 2-5 CP facilitators per CP site for a total of 14 CP facilitators participating in the study, c) 3-4 CP groups per facilitator for a total of 49 CP groups with participants enrolled in the study, and, on average, e) 8 study-enrolled mother-child dyads per CP group, and f) 159 gingival probe sites per mother; the maternal PI data and the child-level MS data will share the first four levels. The total sample size estimate is 392 mother-child dyads (49 CP groups  $\times$  8 mother-child dyads/CP group results in a total of 392 month-child dyads). Power analyses assumed two randomized groups including 8 and 6 CP facilitators, respectively. From our pilot data, we estimated intra-cluster correlations (ICC) for maternal PD4 equal to 0.001 for CP sites, facilitators, and groups, as well as 0.13 for CP women; ICCs for BOP equaled 0.04 for CP sites, facilitators, and groups, as well as 0.27 for CP women; ICCs for maternal PI equaled 0.13 for sites and 0.14 for facilitators and groups; ICCs for the child MS outcome equaled 0.01 for CP sites and CP facilitators as well as 0.04 for CP groups.

	observed effect in pilot	min. detectable effect
BOP: Ctrl v Intv (mothers)	16.7% v 10.7% OR=1.67, power>0.97	16.7% v 11.8% OR=1.50, power=0.80
PD $\geq 4$ mm: Ctrl v Intv (mothers)	20.4% v 17.0%* OR=1.25, power=0.80	20.4% v 17.0%* OR=1.25, power=0.80
PI (means) Ctrl v Intv (mothers)	0.95 v 0.76 d=0.41, power=0.89	0.95 vs 0.78 d=0.37, power=0.80
MS: Ctrl v Intv (children)	24.9% v 6.5% OR=4.77, power=0.97	24.9% v 10.9% OR=2.71, power=0.80

\* observed and minimum detectable effects equivalent w/in rounding;  
d represents a group difference of standardized means

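### AE/SAE inquiry is tied to study visits that differ by arm, and none is scheduled between late pregnancy and about 12 months postpartum

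*Combined protocol and SAP*

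**What the plan says.** Section 9.2 sets a recording period and a method. The period: "The PI will record all events with start dates occurring any time after informed consent is obtained until 7 (for non-serious AEs) or 30 days" (the latter for SAEs), counted from the last day of participation. The method: "At each study visit, the investigator will inquire about the occurrence of AE/SAEs since the last visit". Unanticipated problems are logged continuously.

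The visits are defined in Sections 7.2 to 7.4:

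- Visit 1 (Day 0) is for both arms.
- Visit 2 (Day 14 ± 14) carries the restriction "Takes place among participants in the Intervention arm only".
- Visit 4 (Day 90 ± 21) is headed "Administer Infant Module in Intervention Arms", and Section 6.2 confines both modules to that arm.
- Visits 3 (Day 84 ± 15), 5 (Day 109 ± 21) and 6 (Day 474 ± 90) have no arm restriction.

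Section 4 describes the Visit 5 questionnaire as the last prenatal activity and allows it to be done remotely. The next planned contact with a stated purpose is at infant age of about 10 months: "We will assess eligibility of the infant to participate in the follow-up and confirm mother's intention to complete the final assessment". The infant criterion in Section 5.1 is "healthy with no acute or chronic medical conditions, especially those conditions that may have resulted in hospitalizations".

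On withdrawal, Section 7.5 says: "Women who withdraw from the study will be queried to determine their reasons for withdrawal". Section 7.6 marks unscheduled visits as not applicable, and Section 13 says that patient medical records will not be used. Section 9.1.3 lists congenital anomaly and inpatient hospitalization among the SAE criteria. Neither Table 1 nor Appendix A has a row for AE inquiry.

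**The concern.** Two features of the schedule weaken the inquiry rule.

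First, the rule attaches inquiry to visits that are not the same in the two arms. If it is followed as written, intervention women are asked more often during pregnancy and over shorter look-back periods, and shorter look-back usually means better recall.

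Second, the longest interval between visits contains the birth and nearly all of infancy, when events meeting the listed SAE criteria are most likely to arise. A mother who attends Visit 6 is asked about them roughly a year later. A mother who does not attend is not asked under any stated procedure. Section 5.5.1 lists miscarriage and leaving group care for health-risk reasons among the possible causes of withdrawal, so missing Visit 6 may itself be related to safety.

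The event record has uses. Section 9.1.2 monitors AEs for frequency, Section 9.3.2 makes frequency part of deciding whether an event is unexpected, and Section 9.5 lets concern over the number of SAEs lead to suspended enrollment. Section 10 has the DSMB look at safety data at least yearly. Each of these would work from information that is late for attenders and missing for some non-attenders.

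**Working it through.** **Inputs.** Visit days and windows are from Sections 7.2 to 7.4. Sample size and "75% retention at 12 months" are from Section 12.2. The documents give no AE rate and no figure for AE ascertainment.

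**Sample size.** 49 groups × 8 dyads = 392, as stated.

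**Inquiry points if every visit counts.**

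| | Days | Post-baseline inquiries | Look-back intervals (days) |
|---|---|---|---|
| Intervention | 0, 14, 84, 90, 109, 474 | 5 | 14, 70, 6, 19, 365 |
| Control | 0, 84, 109, 474 | 3 | 84, 25, 365 |

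Both rows of intervals sum to 474 days: 14 + 70 + 6 + 19 + 365 = 474 and 84 + 25 + 365 = 474. Neither arm has calendar time that no inquiry covers. With complete recall, equal true rates would give equal counts.

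**What imperfect recall could do.** This part is an assumption, shown as a range. Let events occur at a uniform rate and let recall halve every h days, with λ = ln 2 / h. The captured fraction over a set of look-back intervals L is Σ[(1 − e^(−λL)) / λ] / ΣL.

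For h = 30 over Days 0 to 109, λ = 0.0231. Intervention: (0.276 + 0.802 + 0.129 + 0.355) / 0.0231 ≈ 67.6 days, and 67.6 / 109 = 0.62. Control: (0.856 + 0.439) / 0.0231 ≈ 56.1 days, and 56.1 / 109 = 0.51. The ratio is 1.21.

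| Assumed h (days) | Captured, Days 0–109, intervention v control | Ratio, Days 0–109 | Ratio, Days 0–474 |
|---|---|---|---|
| 14 | 0.433 v 0.314 | 1.38 | 1.24 |
| 30 | 0.621 v 0.514 | 1.21 | 1.12 |
| 90 | 0.834 v 0.776 | 1.07 | 1.03 |
| 180 | 0.910 v 0.877 | 1.04 | 1.01 |

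If inquiry is confined to Visits 1, 3, 5 and 6, the look-back intervals are identical and the ratio is 1.00 for every h.

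**The gap around birth.**

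- Nominal: 474 − 109 = 365 days.
- Shortest: (474 − 90) − (109 + 21) = 384 − 130 = 254 days.
- Longest: (474 + 90) − (109 − 21) = 564 − 88 = 476 days.

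**Dyads with no Visit 6 inquiry.** 392 × (1 − 0.75) = 98.

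**How far the recording period reaches for a dyad last seen at Visit 5.** The SAE period closes at 109 + 30 = Day 139, or between 88 + 30 = Day 118 and 130 + 30 = Day 160. Visit 6 falls at an infant age of about 12 months, so the nominal schedule puts birth near 474 − 365 = Day 109. Visit 5 is itself prenatal, however, and the Visit 6 window is ± 90 days. For an individual dyad the birth may or may not fall inside the SAE period. Where it does, no planned contact asks about it.

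**The case against.** A reader might infer that AE counts will differ by arm, or that AE rates will be uninterpretable. The documents do not support that. Each inquiry looks back to the previous visit, so coverage is the same, and the ratios above depend entirely on an assumed loss of recall. No between-arm AE comparison is planned, and Section 9.1 directs safety reporting to SAEs and unanticipated problems related to the intervention. This objection stands.

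It is also fair to doubt that anyone asks about AEs at Visits 2 and 4. These are group sessions led by facilitators, and they list only module delivery and the recording of attendance (and, at Visit 2, participation). If nobody asks, the arms are equal, but the rule in Section 9.2 is then not followed as written. The text needs correcting either way.

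A reader might further infer that mothers of ineligible infants drop out of safety inquiry. Section 4 says otherwise: such a mother can still complete the final assessment. Section 4 is silent on whether an illness disclosed at the 10-month contact is recorded, and Section 9.2 would oblige recording of an event that falls within the period. Similarly, Section 7.5 is titled as a visit, so a literal reading of Section 9.2 could extend inquiry to it, although the only content stated is the reason for leaving.

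The 98 dyads are not 98 dyads with promised data missing. The SAE period ends 30 days after last participation, so for those who stop at Visit 5 most of infancy, and possibly the birth, lies outside it. The 75% is a planning assumption for power. The 5-working-day clock in Section 9.4.1 applies only to unanticipated problems that are SAEs, so most unrelated obstetric events would not start it.

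Other routes to recording exist: continuous logging of unanticipated problems, and facilitators' awareness of women's condition. They are passive, and the second is described only for the facilitator who delivers the intervention. They narrow the gap without closing it. The Manual of Procedures, held separately, may say more. Section 5.6 reports minimal-risk pilots without adverse events, which limits the stakes.

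**Conclusion.** The point holds as a weakness in how safety information is collected.

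- **Unequal inquiry.** Read literally, Section 9.2 produces five post-baseline inquiries against three. This is a risk of differential ascertainment in pregnancy. Its size is unknown: a capture ratio of 1.04 to 1.38 over Days 0 to 109 for assumed recall half-lives of 180 down to 14 days, and 1.00 with full recall or if no one asks at Visits 2 and 4.
- **Birth period.** No inquiry is scheduled for 365 days nominally (254 to 476). Birth-period SAEs depend on about a year's recall in dyads who attend Visit 6. About 98 of 392 dyads, if 75% retention holds, would have no planned inquiry about the birth, although part of that time may lie outside the recording period for those who stop at Visit 5.

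The consequence is that SAE information reaching the DSMB, and available for halting decisions under Section 9.5, would be late and incomplete. The primary and secondary efficacy analyses and the sample size are unaffected. The change is worth making because it is cheap and uses contacts already planned.

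**What to change.** In Section 9.2, name the AE/SAE inquiry points and make them the same in both arms: Visits 1, 3, 5 and 6, with one scripted set of questions that also works when Visit 5 is done remotely. Record events reported spontaneously at other times, including at the module sessions, and keep them identifiable as such.

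Add the same scripted SAE questions to the existing 10-month contact for every mother and infant, including those who will not attend Visit 6. State in Section 7.5 that the withdrawal query includes them. State that an infant's ineligibility for saliva collection does not end safety recording for that infant. Say how the end of the recording period in Section 9.2 applies to dyads who stop before Visit 6 but are reached at 10 months. Add an AE inquiry row to Appendix A.

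The cost is protocol wording, a short script, a few minutes per contact, and more unrelated obstetric and infant events to log and assess. The sample size stays at 392.

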### **9.3 Characteristics of an Adverse Event**

#### ***9.3.1 Relationship to Study Intervention***

To assess relationship of an event to study intervention, the following guidelines are used:

1. Related (Possible, Probable, Definite)
  - a. The event is known to occur with the study intervention.
  - b. There is a temporal relationship between the intervention and event onset.
  - c. The event abates when the intervention is discontinued.
  - d. The event reappears upon a re-challenge with the intervention.
2. Not Related (Unlikely, Not Related)
  - a. There is no temporal relationship between the intervention and event onset.
  - b. An alternate etiology has been established.

#### ***9.3.2 Expectedness***

The PIs will be responsible for determining whether an AE is expected or unexpected. An adverse event will be considered unexpected if the nature, severity, or frequency of the event is not consistent with the risk information previously described for the intervention.

#### ***9.3.3 Severity of Event***

The following scale will be used to grade adverse events:

1. Mild: no intervention required; no impact on activities of daily living (ADL)
2. Moderate: minimal, local, or non-invasive intervention indicated; moderate impact on ADL
3. Severe: significant symptoms requiring invasive intervention; subject seeks medical attention, needs major assistance with ADL

## 9.4 Reporting Procedures

Federal regulations and the UCSF IRB/HRPP require investigator reporting of any post-approval research-related event or information that may meet the HRPP's institutional definitions of "unanticipated problem involving risk to participants or others" or "serious or continuing noncompliance." The IRB/HRPP reviews the reports and determines whether they meet the institutional definition of a UP, among other things.

### 9.4.1 UP Reporting to IRB and NIDCR

Incidents or events that meet the OHRP criteria for unanticipated problems require the creation and completion of an unanticipated problem report form. OHRP recommends that investigators include the following information when reporting an AE, or any other incident, experience, or outcome as an UP to the IRB:

- appropriate identifying information for the research protocol, such as the title, investigator's name, and the IRB project number;
- a detailed description of the adverse event, incident, experience, or outcome;
- an explanation of the basis for determining that the adverse event, incident, experience, or outcome represents an unanticipated problem;
- a description of any changes to the protocol or other corrective actions that have been taken or are proposed in response to the unanticipated problem.

To satisfy the requirement for prompt reporting, UPs will be reported using the following timeline:

- UPs that are SAEs will be reported to the IRB and to NIDCR within 5 working days of the investigator becoming aware of the event.
- Any other UP will be reported to the IRB and to NIDCR within 10 working days of the investigator becoming aware of the problem.
- All UPs should be reported to appropriate institutional officials (as required by an institution's written reporting procedures), the supporting agency head (or designee), and OHRP within one month of the IRB's receipt of the report of the problem from the investigator.

All UPs will be reported to NIDCR's centralized reporting system via Rho Product Safety:

- Product Safety Fax Line (US): [name]
- Product Safety Fax Line (International): [contact]
- Product Safety Email: [rho\\[contact]](mailto:[contact])

General questions about SAE reporting can be directed to the Rho Product Safety Help Line (available 8:00AM – 5:00PM Eastern Time):

- US: [name]
- International: [contact]

